11.1.3. Crohn's Disease Activity Index

The Crohn's Disease Activity Index (CDAI) is a composite score that is used to measure the clinical activity of Crohn's disease. The CDAI uses a questionnaire with responses scored numerically and weighted. Scores range from 0 to approximately 600, with higher scores indicating greater disease activity. The 8 components used to assess the CDAI and their weighting factors are noted in [Table 6](#). The definitions of mild, moderate, and severe Crohn's disease are provided in [Table 7](#).

Patient-reported outcomes (stool frequency and abdominal pain components of the CDAI Score and general well-being), and the other CDAI components will be collected in an electronic diary. Patients will complete the stool frequency, abdominal pain and general well-being components of the CDAI from the patient’s first screening visit and will continue throughout the trial.

Patients will be instructed on the use and completion of questions on the electronic diary.

The diary entries will be reviewed by site personnel during screening (prior to dosing, if applicable) and during all trial visits. The stool frequency and abdominal pain diary entries preceding each trial visit will be used to calculate the CDAI score and will be calculated using the stool frequency and the abdominal pain data from the most recent 7 day period, or at least 3 days within that 7 day period, prior to the visit, excluding the following:

- One day prior to the start of a procedure or preparation for a procedure that would affect stool frequency
- The day(s) of a procedure or preparation for a procedure that would affect stool frequency

Because the colonoscopy preparations can interfere with the assessment of other clinical parameters, diary entries used to calculate the CDAI score will not correspond to day(s) of bowel preparation or endoscopy.

Table 6: CDAI Assessment

| Clinical or Laboratory Variable | Weighting Factor, × |
|---|----------------------------|
| Number of liquid or soft stools each day for 7 days | 2 |
| Abdominal pain (graded from 0-3 on severity) each day for 7 days | 5 |
| General well-being, assessed from 0 (well) to 4 (terrible) daily for 7 days | 7 |
| Presence of complications* | 20 |
| Taking diphenoxylate/atropine, loperamide, or opiates for diarrhea | 30 |
| Presence of an abdominal mass (0 as none, 2 as questionable, 5 as definite) | 10 |
| Hematocrit 47-HCT in men and 42-HCT in women | 6 |

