4.2.1. Definitions

Table 2. Key Terms

Term	Definition
SES-CD	The sum of the scores for the 5 segments composed of the sum of 4 separate components that include: Size of ulcers, Extent of ulcerated surface, Extent of affected surface and the presence and type of narrowing. The 4 components are evaluated for each of the accessible segments and are scored as 0 to 3. The segments include: rectum, sigmoid & left colon, transverse colon, right colon and the ileum. The range of SES-CD scores is 0 – 12 for each segment, and 0 – 56 for the overall SES-CD score, with larger scores indicating greater severity of disease.
CDAI	The weighted sum of the 8 components: Number of liquid or soft stools for 7 days, Abdominal pain for 7 days, general well-being for 7 days, presence of complications, taking diarrhea medication, abdominal mass, hematocrit and percentage deviation from standard weight. The typical range of CDAI score is 0 to > 600 .
PRO2	The weighted sum of two items that separately contribute to the derivation of two CDAI sub-scores: $PRO2 = SF*7*2 + AP*7*5$. See Table 10, Appendix 3 for details.
SF/AP	The unweighted sum of two items that separately contribute to the derivation of two CDAI sub-scores: $SF/AP = SF + AP$. See Table 10, Appendix 3 for details. NOTE: This definition is included for reference only; in some clinical trials for Crohn’s disease, this has been used for various endpoints.
SF&AP	SF & AP Remission, defined as Average daily stool score ≤ 3 points AND average daily abdominal pain score ≤ 1 point
GHAS	Geboes Histology Activity Score
RHI	Robarts Histopathology Index

Table 3. Key Endpoints

Category or Shorthand	Label	Definition
Endoscopy	Endoscopic Change	SES-CD change from baseline
	Endoscopic Response-25	SES-CD decrease from baseline of $\geq 25\%$
	Endoscopic Response-50	SES-CD decrease from baseline of $\geq 50\%$
	Endoscopic Remission	SES-CD ≤ 4 points and a SES-CD decrease from baseline ≥ 2 points with no SES-CD sub-score > 1 point
CDAI	CDAI Change	CDAI change from baseline
	SF Change	SF Change from baseline
	AP Change	SF Change from baseline
	CDAI Clinical Response	CDAI decrease from baseline of ≥ 100 points
	CDAI Clinical Remission	CDAI score of <150
PRO2	PRO2 Clinical Response	PRO2 CD decrease $\geq 50\%$
SF&AP	SF & AP Remission	Average daily stool score ≤ 3 points AND average daily abdominal pain score ≤ 1 point
Histology	GHAS Change	GHAS change from baseline

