4.2.3. Efficacy Endpoints for Extension Period

The efficacy endpoints for the induction period listed above in section 4.2.2 will be evaluated for all extension visits.

In addition, proportion of patients achieving remission and remaining corticosteroid-free in the prior 12 weeks will be evaluated at each time point of Week 36, Week 48, and Week 52, among the patients who received corticosteroids for CD at baseline. This analysis will be performed for CDAI Remission and SF&AP Remission.

Clinical Remission (Based on CDAI) at both Week 12 and Week 52 will also be summarized. Following efficacy graphs will be presented.

- CDAI change from Baseline (Observed) showing mean and 95% CI at each scheduled visit up to Week 52, overall and by Biologic Exposed vs. Biologic Naïve
- CDAI (Observed) showing mean and 95% CI at each scheduled visit up to Week 160, overall and by Biologic Exposed vs. Biologic Naïve
- Bar graph of CDAI Clinical Response (NRI) at Week 12 and Week 52, overall and by Biologic Exposed vs. Biologic Naïve
- Bar graph of CDAI Clinical Response (Observed) at Week 12 and Week 52, overall and by Biologic Exposed vs. Biologic Naïve
- Bar graph of CDAI Clinical Remission (NRI) at Week 12 and Week 52, overall and by Biologic Exposed vs. Biologic Naïve
- Bar graph of CDAI Clinical Remission (Observed) at Week 12 and Week 52, overall and by Biologic Exposed vs. Biologic Naïve
- Bar graph of Endoscopic Response-50 (Paired Segments, NRI) at Week 12 and Week 52, overall and by Biologic Exposed vs. Biologic Naïve
- Bar graph of Endoscopic Response-50 (Paired Segments, Observed) at Week 12 and Week 52, overall and by Biologic Exposed vs. Biologic Naïve
- Stool frequency change from Baseline (Observed) showing mean and 95% CI at each scheduled visit up to Week 52, overall and by Biologic Exposed vs. Biologic Naïve
- Stool frequency (Observed) showing mean and 95% CI at each scheduled visit up to Week 160, overall and by Biologic Exposed vs. Biologic Naïve

- Abdominal Pain change from Baseline (Observed) showing mean and 95% CI at each scheduled visit up to Week 52, overall and by Biologic Exposed vs. Biologic Naïve
- Abdominal Pain (Observed) showing mean and 95% CI at each scheduled visit up to Week 160, overall and by Biologic Exposed vs. Biologic Naïve

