5.3. Statistical Hypotheses and Multiple Endpoint Handling

No statistical hypothesis testing will be performed in this trial.

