5.5. Other Important Considerations

5.5.1. Definition of Baseline

Unless otherwise specified, baseline is defined as the last observation collected on or before the receipt of first dose of Investigational Product (IP). Calculation of Change and Percent Change from Baseline are done according to the following:

- Change from Baseline to any trial Week t (C_t) is calculated as follows:
 - $C_t = M_t - M_B$, where:
 - M_t is the measurement of interest at Week t
 - M_B is the measurement of interest at Baseline
- Percent change from Baseline to any trial Week t (P_t) is calculated as follows:
 - $P_t = 100 * (C_t / M_B)$

NOTE: If $M_B = 0$ or missing then percent change from Baseline will not be determined.

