APPENDIX 3. CDAI SCORE CALCULATIONS

The Crohn’s Disease Activity Index (CDAI) is a composite score that is used to measure the clinical activity of Crohn’s disease. The CDAI uses a questionnaire with responses scored numerically and weighted. Scores typically range from 0 to approximately 600, with higher scores indicating greater disease activity. The 8 components used to assess the CDAI, their weighting factors and calculation rules are noted in the table below. The number of stools, abdominal pain and general well-being are patient-reported outcomes which will be entered daily into an e-diary by patients. The Hematocrit component will be coming from the lab data and the other 4 components will be entered by the site at each visit.

Table 10. Score calculations, weights, and rules associated with CDAI, its components, and associated endpoints

Item	Weight	Algorithm

Number of liquid or soft stools (CDAI sub-score)
	
2
	
 • Use the most recent 7 days prior to the visit date in Rave EDC database; excluding the day prior and the day of the endoscopy, as applicable. • Define: SF = average daily stool score = average of the number of liquid/soft stools for the available days in the 7-day window • If there are less than 3 days with non-missing values, then set SF to missing • If there are 7 days of data available, then the CDAI sub-score is equal to the sum of the 7 days*2; otherwise, the CDAI sub-score is equal to the average daily stool score*7*2; as a formula, this is written as $\text{CDAI sub-score} = \text{SF} * 7 * 2$ in both cases

Abdominal pain (CDAI sub-score)
	
5
	
 • Use the most recent 7 days prior to the visit date in Rave EDC database; excluding the day prior and the day of the endoscopy, as applicable. • Define: AP = average daily abdominal pain score = average of the abdominal pain level for the available days in the 7-day window • If there are less than 3 days with non-missing values, then set AP to missing

		
 If there are 7 days of data available, then the CDAI sub-score is equal to the sum of the 7 days*5; otherwise, the CDAI sub-score is equal to the average daily abdominal pain score*7*5; as a formula, this is written as CDAI sub-score = AP*7*5 in both cases

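### SAP Table 3 gives the AP Change endpoint the stool-frequency definition, an apparent copy error that conflicts with Appendix 3 and with the planned abdominal-pain graphs

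*SAP*

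**What the plan says.** SAP section 4.2.1, Table 3, assigns a label and a definition to each key endpoint. Under the CDAI category, SF Change and AP Change stand on consecutive rows, and both definitions read "SF Change from baseline".

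The two labels are then used as separate endpoints:

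- SAP 4.2.2 lists SF Change and AP Change as two of the other efficacy endpoints for the Induction Period, by label only.
- SAP 4.2.3 carries the induction endpoints forward to all extension visits. It also plans graphs of abdominal pain, including "Abdominal Pain change from Baseline (Observed) showing mean and 95% CI at each scheduled visit up to Week 52", separately from the stool-frequency graphs.
- SAP 9.3, Table 5, gives each label its own row, analysed on observed cases, without restating a definition.

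Appendix 3, Table 10, defines the underlying variables: "SF = average daily stool score" and "AP = average daily abdominal pain score". The SAP's abbreviation list likewise expands AP as abdominal pain.

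**The concern.** Table 3 is the only place in the available text that expressly says what the label AP Change means, and it names the wrong variable. This is the definition of a listed efficacy endpoint, not background. The protocol supplies no substitute. The visible endpoint lists in protocol 6.2 contain no change endpoint for stool frequency or abdominal pain. Protocol 11.1.5 says the unweighted items will serve as efficacy endpoints, but it points to 11.1.7, which gives only response and remission definitions.

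At stake is one descriptive endpoint. If the table were programmed from the printed definition, the AP Change summary would show stool frequency under an abdominal-pain label. The abdominal-pain change graph stops at Week 52, and from there to Week 160 only actual values are graphed. After Week 52 the by-visit table would therefore be the only planned summary of abdominal-pain change, and it would hold the wrong variable.

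**Working it through.** There is no plan figure to reproduce, and no power or sample-size calculation applies. The check sets the definitions side by side.

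**Inputs**

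| Item | Source | Content |
|--|--|--|
| SF | SAP Appendix 3 | average daily stool score |
| AP | SAP Appendix 3 | average daily abdominal pain score |
| Change rule | SAP 5.5.1 | C_t = M_t − M_B, where M_t "is the measurement of interest at Week t" and M_B is its baseline value |
| SF Change, as printed | SAP Table 3 | change in SF |
| AP Change, as printed | SAP Table 3 | change in SF |
| Daily pain scale | Protocol 11.1.3, Table 6 | "Abdominal pain (graded from 0-3 on severity) each day for 7 days" |

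**Step 1. As printed.** Putting the Table 3 definition into the change rule gives AP Change = SF_t − SF_B. This is identical to SF Change for every patient and visit.

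**Step 2. As the rest of the SAP intends.** With M = AP, AP Change = AP_t − AP_B. Each daily pain grade lies between 0 and 3, so the average does too. The change must then lie between 0 − 3 = −3 and 3 − 0 = +3. A change in stool count has no such bound, so the two are different quantities on different scales.

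**Step 3. Illustration, with assumed values that are not from the documents.** Suppose SF goes from 6 to 3 and AP from 2 to 1.

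- SF Change = 3 − 6 = −3.
- AP Change as printed = 3 − 6 = −3, the same number.
- AP Change as intended = 1 − 2 = −1.

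**Step 4. How far it reaches.** Table 5 has nine rows: Endoscopic Change, CDAI Change, SF Change, AP Change, GHAS Change, RHI Change, CRP Change, FCP Change and Global RHI Score. One of the nine is affected. The other endpoints that involve abdominal pain take AP directly from Appendix 3 or have their own wording:

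- CDAI uses AP × 7 × 5 as a sub-score.
- PRO2 = SF × 7 × 2 + AP × 7 × 5.
- SF&AP Remission is written out in full in Table 3, in terms of the two average daily scores.

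None of them uses AP Change. The primary endpoint, change in SES-CD, is unrelated.

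**Step 5. Could this be a PDF-reading fault?** Labels and definitions line up in the neighbouring rows, nothing in these rows is redacted, and this is current text rather than revision history. The two definitions also share a capitalised *Change* that the other change-from-baseline rows of the table do not have. A copied cell is the natural explanation.

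**The case against.** The strongest reply is that nobody would be misled. The row label, the abbreviation list, Appendix 3 and the general change rule together determine AP Change completely. Two separately named endpoints with one definition are visibly a slip, not a choice between analyses. The SAP nowhere gives Table 3 precedence over Appendix 3, and section 4.2 sends the reader to that appendix for the average daily scores. The endpoint is also descriptive, and SAP 5.3 states: "No statistical hypothesis testing will be performed in this trial". All of this stands, and it limits the weight of the point. It does not make the printed definition correct.

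Two stronger readings are tempting, and the documents do not support them.

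- **That abdominal-pain change would go unreported.** A reader might infer this from Table 3 alone. Section 4.2.3 separately requires graphs of abdominal-pain change to Week 52 and of actual abdominal-pain values to Week 160, with the variable named in full. Even under a literal reading, the loss is confined to the AP Change summary in the by-visit tables.
- **That SF&AP Remission is compromised because abdominal pain is one of its two parts.** That endpoint has its own complete definition and does not use AP Change, so the error does not pass into it.

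**Conclusion.** The point holds as an editorial error in an operative definition, at the lowest severity. As printed, one of nine continuous endpoints duplicates another at every visit and contradicts the planned abdominal-pain graphs. No test, decision or sample size depends on it.

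This rests on two assumptions. The first is that the table text was read correctly from the PDF, which the surrounding rows support. The second is that no table shell or programming specification already overrides the definition; those documents were not available. If one does, the error remains in the SAP but would not reach the output.

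**What to change.** In SAP Table 3, replace the AP Change definition with: *AP (average daily abdominal pain score) change from baseline*. The minimum correction is two letters, SF to AP. Naming the score in full also makes clear that the 0 to 3 daily average is meant and not the weighted CDAI sub-score, which is 7 × 5 = 35 times as large. That is worth stating because the endpoint sits under the CDAI category.

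The change alters no planned figure, sample size or other endpoint. If outputs already exist, confirm that the AP Change table differs from the SF Change table and agrees with the abdominal-pain change graph through Week 52.

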8. SELECTION AND WITHDRAWAL OF PATIENTS

8.1. Patient Inclusion Criteria

To be eligible to participate in this trial, candidates must meet the following inclusion criteria:

1. Male or female patients aged 18 to 75 years, inclusive
2. Diagnosis of Crohn's disease for at least 2 months (prior to Screening) by clinical endoscopic evidence and corroborated by a histology report (Note: histopathology may be performed during Screening if no prior report is readily available).
3. Crohn's disease Activity Index score of 220 to 450 inclusive with an SES-CD score of ≥ 6 . (If disease isolated to ileum, the requirement will be a SES-CD score ≥ 4 .)
4. Average daily stool score ≥ 4 points and/or an average daily abdominal pain score of ≥ 2 points.
5. Patients must meet one of the following criteria:
 - Have an inadequate response or loss of response to at least one of the following Crohn's disease treatments :
 - Aminosalicylates, oral aminosalicylates ≥ 2.4 g/day or ≥ 3 g/day sulfasalazine for at least 4 weeks
 - Corticosteroids, oral prednisone ≥ 30 mg or budesonide ≥ 9 mg for at least 2 weeks or an equivalent (to oral prednisone) of intravenous corticosteroid for 1 week
 - Immunomodulators, oral azathioprine ≥ 1.5 mg/kg or 6-mercaptopurine 0.75 mg/kg (documentation of therapeutic level of 6-thioguanine is also acceptable) or methotrexate ≥ 12.5 mg/week for at least 8 weeks
 - Biologic therapy (TNF α antagonist or vedolizumab only) at an approved labeled dose used for induction therapy for at least 4 weeks or recurrence of disease activity despite scheduled maintenance therapy. (Biologic therapy exposed patients will be capped at 50% of total enrolled patients)
 - And/or have been intolerant to any of the above mentioned therapies (e.g., unable to achieve doses, dose levels, or treatment durations because of treatment related side effects and/or laboratory abnormalities)
6. The following background therapies for Crohn's disease will be permitted on a stable dose:
 - Oral aminosalicylates (e.g., mesalamine, sulfasalazine, olsalazine, balsalazide) at a stable dose for at least 3 weeks prior to Screening endoscopy
 - Prednisone (doses ≤ 20 mg per day) or equivalent at a stable dose (dose ≤ 9 mg per day) for at least 2 weeks prior to Screening endoscopy
 - Budesonide therapy at a stable dose for at least 2 weeks prior to Screening endoscopy

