	GHAS Remission	No active inflammation in any measured segment; see Appendix 4 for details
	RHI Change	RHI change from baseline
	RHI Response - by Segment	RHI segment score decrease $\geq 50\%$
	RHI Remission- by Segment	No active inflammation in a measured segment
	RHI Remission	No active inflammation in any measured segment; see Appendix 4 for details
	Global RHI Score	A weighted sum of the worst of each of the four disease components across the four colonic segments; see Appendix 4 for details
Mucosal Healing	RHI Mucosal Healing	Endoscopic Remission combined with RHI Remission
Biomarkers	CRP Change	C-reactive protein change from baseline
	CRP Response-10	C-reactive protein < 10 mg/L
	FCP Change	Fecal calprotectin change from baseline
	FCP Response-250	Fecal calprotectin < 250 mcg/g

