4.2.2. Efficacy Endpoints for Induction Period

Primary Efficacy Endpoint

- Endoscopic Change

Other Efficacy Endpoints

- Category: Endoscopy

- Proportion of patients with Endoscopic Response-25
- Proportion of patients with Endoscopic Response-50
- Proportion of patients with Endoscopic Remission
- Category: CDAI
 - CDAI Change
 - SF Change
 - AP Change
 - Proportion of patients with CDAI Clinical Response
 - Proportion of patients with CDAI Clinical Remission
- Category: PRO2
 - Proportion of patients with PRO2 Clinical Response
- Category: SF&AP
 - Proportion of patients with SF&AP Remission
- Category: Histology
 - GHAS Change
 - Proportion of patients with GHAS Remission
 - RHI Change
 - Global RHI Score Change
 - Proportion of patients with RHI Response - by segment among non-RHI remitters at Baseline
 - Proportion of patients with RHI Remission
 - Proportion of patients with RHI Remission - by segment
 - Proportion of patients with RHI Remission - by segment among non-RHI remitters at Baseline
- Category: Mucosal Healing
 - Proportion of patients with RHI Mucosal Healing
- [REDACTED]
- [REDACTED]
- [REDACTED]
- [REDACTED]
- [REDACTED]
- [REDACTED]

– [REDACTED]

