APPENDIX 4. GEBOES HISTOLOGY ACTIVITY INDEX AND ROBARTS HISTOPATHOLOGY INDEX

The following tables give details of the scoring for the Global Histologic Disease Activity Score (GHAS)^{3,4} and a newly developed scoring system entitled the Robarts Histopathology Index (RHI)⁵. Higher numbers correspond to more inflammation and mucosal damage. For each CD segment, the GHAS score can be treated as a continuous measure on a 16 point scale. For each CD segment, the RHI score can be treated as a continuous measure on a 33 point scale. Scoring for both indices will be performed for each segment (i.e., ileum, right, transverse, left (descending and sigmoid), and rectum) that is visualized and for which biopsy samples are available. Similar to the SES-CD, sub-scores for each segment will be derived.

The eight components used to assess the per-CD segment GHAS score are noted in the table below. The maximum per-CD segment total score is 16.

Table 11. GHAS Grading System

GHAS Descriptors and Levels	
Epithelial damage	0: Normal 1: Focal Pathology 2: Extensive Pathology
Architectural changes	0: Normal 1: Moderately disturbed (<50%) 2: Severely disturbed (>50%)
Infiltration of mononuclear cells in the lamina propria	0: Normal 1: Moderately increase 2: Severe increase
Infiltration of polypmorphonuclear cells in the lamina propria	0: Normal 1: Moderately increase 2: Severe increase
Polypmorphonuclear cells in epithelium	0: Normal 1: In surface epithelium 2: Cryptitis 3: Crypt abscess
Presence of erosion and/or ulcers	0: No 1: Yes
Presence of granuloma	0: No 1: Yes
Number of biopsy specimens affected	0: None (0 of 6) 1: ≤3% (1 or 2 of 6) 2: 33-66% (3 or 4 of 6) 3: >66% (5 or 6 of 6)

1

[REDACTED]

Exploratory GHAS Histologic Remission (no active inflammation in a measured segment) is defined in the following table, where the max overall GHAS score in a given segment must be less than or equal to 8, and each segment meets this standard:

Table 12. Per-CD Segment GHAS Scores Allowed for Histologic Remission

Epithelial damage	0
Architectural changes	0-2
Infiltration of mononuclear cells in the lamina propria	0-2
Infiltration of polymorphonuclear cells in the lamina propria	0
Polymorphonuclear cells in epithelium	0
Presence of erosion and/or ulcers	0
Presence of granuloma	0-1
Number of biopsy specimens affected	0-3

The four components used to assess the per-CD segment RHI score are noted in the table below. The maximum per-CD segment total score is 33.

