Table 13. Roberts Histopathology Index (RHI) Grading System

Subcomponent Descriptors	Scores	Weighting factor
Chronic inflammatory infiltrate	0=No increase 1=Mild but unequivocal increase 2=Moderate increase 3=Marked increase	1
Lamina propria neutrophils	0= None 1= Mild but unequivocal increase 2=Moderate increase 3=Marked increase	2
Neutrophils in epithelium	0=None 1 = <5% crypts involved 2= <50% crypts involved 3= >50% crypts involved	3
Erosion or ulceration	0=No erosion, ulceration or granulation tissue 1=Recovering epithelium + adjacent inflammation OR probable erosion-focally stripped 2=Unequivocal erosion 3=Ulcer or granulation tissue	5

An exploratory RHI Histologic Remission (no active inflammation in a measured segment) is defined in the following table. The maximum per-CD segment RHI score allowable for a segment to qualify for RHI Histologic Remission is 3. A patient not meeting at least one of the criteria 2, 3, or 4, below in a segment is defined as a non-RHI remitter for that segment. Note that criteria 1 is always met.

Table 14. Per-CD Segment RHI Scores Allowed for Histologic Remission

Subcomponent Descriptors	Scores	Weighting factor
Chronic inflammatory infiltrate	0-3	1
Lamina propria neutrophils	0	2
Neutrophils in epithelium	0	3
Erosion or ulceration	0	5

Global RHI Score

Global RHI Score is a weighted sum of the worst, i.e., the highest, of each of the four disease component scores across the four colonic segments, rectum, left colon, transverse colon, and right colon. Same weighting factors used in computing the RHI Score is used.

Global RHI Score = 1x highest Chronic inflammatory infiltrate score + 2x highest Lamina propria neutrophils score + 3x highest Neutrophils in epithelium score + 5x highest Erosion or ulceration score.

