APPENDIX 5. DOCUMENT REVISION HISTORY

Version	Date	Notes/Revisions
1.0	March 03 2016	Initial version.
1.1	November 23 2016	Updated with details and additional analyses.
1.2	January 26 2017	Updated with details on missing data and other details.
1.3	June 1, 2018	
Updated to reflect the Week 12 and Week 52 summary tables generated for topline analyses, definition of treatment failure, as well as to reflect endpoint alterations and additional details regarding CDAI, SES-CD, GHAS, and RHI algorithms. Analysis of compliance rate categories has been excluded.
 
Following endpoints have been removed from the SAP
 
 • PRO CD SF+AP response-25 • PRO CD SF+AP response-50 • PRO CD SF+AP response-30 + 2P • PRO2 CD response-25 • SF&AP clinical response-2 • SF&AP clinical response-1 • Endoscopic remission-2 • Histologic improvement • Histologic response 
Following endpoints have been added to the SAP
 
 • CRP-response-10 • FCP response-250 • Fistula Response • GHAS Improvement • GHAS Remission • RHI Improvement • RHI Response • RHI Remission • Global RHI Score • RHI Mucosal Healing
1.4	August 28, 2019	
LOCF removed.
 
Treatment Failure rule is used in NRI
 
Efficacy graphs added

1.5	January 06, 2020	
Changes from data review meeting
 
 • PFT abnormality has been revised • Missing segment imputation of SES-CD has been added

		
• Lower bound of 0 for Hematocrit sub-score of CDAI has been added• Treatment failure criteria has been revised• RHI response analysis on all patients has been removed• RHI remission by segment for subset of segment score > 3 is replaced by RHI remission by segment for non-RHI remitters• CRP Change among patients having CRP \geq 10 mg/L at Baseline has been added• Analysis window has been added to Safety follow-up visits• Unscheduled and early termination visits are included in all analysis windows• Patients requiring cardiac monitoring is determined programmatically• Listing of non-trial procedures added• Section on PK analysis is removed and combined with Section on PD• Description of SDTM data in Section 5 is removed
--	--	---

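### The exploratory patient-level RHI and GHAS Remission proportions can count patients already inactive on histology at baseline as successes; add a version among baseline non-remitters

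*SAP*

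**What the plan says.** **Definition.** SAP 4.2.1, Table 3, gives GHAS Remission and RHI Remission the same wording: "No active inflammation in any measured segment; see Appendix 4 for details". Appendix 4 adds score limits only. For GHAS, "the max overall GHAS score in a given segment must be less than or equal to 8, and each segment meets this standard", and Table 12 sets epithelial damage, both neutrophil items and erosion to 0. For RHI, "The maximum per-CD segment RHI score allowable for a segment to qualify for RHI Histologic Remission is 3", with the neutrophil and erosion items at 0 (Table 14). None of this refers to baseline.

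**Endpoint list.** SAP 4.2.2 lists "Proportion of patients with GHAS Remission" and the matching RHI item without restriction, and 4.2.3 carries both into the Extension Period. The list restricts on baseline status only at segment level and only for RHI: once for RHI Response, and once as "Proportion of patients with RHI Remission - by segment among non-RHI remitters at Baseline". Appendix 4 supplies the rule, and the status it assigns attaches to the single segment: "A patient not meeting at least one of the criteria 2, 3, or 4, below in a segment is defined as a non-RHI remitter for" [...]. The revision history (Appendix 5, version 1.5) also speaks only of segments: "RHI remission by segment for subset of segment score > 3 is replaced by RHI remission by segment for non-RHI remitters".

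**Population and missing data.** Efficacy uses the ITT population with all its patients in the denominator (SAP 5, 5.4, 9). Missing data and responses after treatment failure count as non-response in the primary analysis of proportions (5.5.4, 9.4). The paired-segment rule (5.5.5) removes segments that could not be evaluated at baseline, not segments that were inactive.

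**Entry.** Protocol 8.1 requires a CDAI "score of 220 to 450 inclusive with an SES-CD score of ≥ 6" (at least 4 for disease confined to the ileum) and a symptom threshold. Histology is needed only to support the diagnosis, and a prior report is enough.

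**The concern.** An endpoint defined only by status at the visit measures achievement only if nobody holds that status at the start. CDAI Clinical Remission meets this condition through entry: remission is below 150 and entry starts at 220. Endoscopic Remission meets it by definition, because it also demands a fall of at least 2 SES-CD points. Patient-level RHI and GHAS Remission have neither safeguard.

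The trial has a single arm, so no control rate shows how much of a histologic remission proportion was there before treatment. A reader who sees only the ITT proportion cannot separate patients who changed from patients who were never active in the segments measured. The SAP deals with this for two by-segment RHI endpoints but, in the visible text, not for the patient-level proportions and not for GHAS at all.

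**Working it through.** **1. The plan's own figures.**
- RHI segment maximum: 3 × (1 + 2 + 3 + 5) = 33. Remission maximum: 3 × 1 = 3. Both agree with Appendix 4.
- GHAS segment maximum: 2 + 2 + 2 + 2 + 3 + 1 + 1 + 3 = 16. Remission maximum under Table 12: 0 + 2 + 2 + 0 + 0 + 0 + 1 + 3 = 8. Both agree.
- SAP 5.1 precision, from 1.96 × √[p(1 − p)/n]: at n = 60, p = 15% gives 9.03% and p = 30% gives 11.60%; at n = 30, 12.78% and 16.40%. These match the stated values.

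The score limits confirm that remission depends on the visit's histology alone.

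**2. Can a patient be in remission at baseline?** Every measured segment must be inactive despite SES-CD ≥ 6 (≥ 4 if ileal only). That is a demanding condition, but nothing forbids it. One possible route is ileum-only disease. The protocol (Tables 2 and 3, Section 11.1.2) speaks of colonic biopsies and leaves the details to a biopsy manual. SAP Appendix 4 scores a segment, the ileum included, only where biopsies are available. A patient with ileal disease and no ileal sample could be inactive in all measured segments. Whether this happens depends on the manual, which is not among the documents.

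**3. Effect on the reported rate.** Let
- p0 = share of ITT patients in histologic remission at baseline (not in the documents);
- s = share of those counted as remitters at the visit under NRI, that is, still inactive, observed and not treatment failures (not in the documents);
- r = remission rate among patients active at baseline.

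Reported rate = p0·s + (1 − p0)·r, so reported rate − r = p0(s − r).

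With r = 15% (the remission rate assumed in SAP 5.1) and 60 patients, the excess in percentage points is:

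| Baseline remitters (assumed) | p0 | s = 100% | s = 80% | s = 50% |
|---|---|---|---|---|
| 3 | 5% | 4.25 | 3.25 | 1.75 |
| 6 | 10% | 8.5 | 6.5 | 3.5 |
| 9 | 15% | 12.75 | 9.75 | 5.25 |
| 12 | 20% | 17.0 | 13.0 | 7.0 |

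For example, 6 patients with s = 80%: 0.10 × (0.80 − 0.15) = 6.5 points, a reported rate of 21.5% against 15%.

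**4. Limiting case, r = 0.** Six baseline remitters all stay inactive and are observed, and no active patient remits. The SAP reports 6/60 = 10.0%, Clopper-Pearson 95% CI 3.8 to 20.5. Among the 54 active patients the result is 0/54, with upper limit 1 − 0.025^(1/54) = 6.6%. Each such patient adds 1/60 = 1.7 points.

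**5. Direction.** If s < r the sign reverses. With p0 = 10%, r = 15% and s = 10%: 0.10 × (0.10 − 0.15) = −0.5 points.

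**The case against.** **Exploratory status.** SAP 9.2.2 and Appendix 4 label these endpoints and definitions exploratory. The primary endpoint is SES-CD change, and no hypothesis is tested. This stands and sets the priority.

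**Likely small p0.** A single inactive segment is ordinary in patchy disease; all measured segments inactive together is much rarer in patients who met the SES-CD threshold. The by-segment restriction may therefore reflect where the problem was seen, not an oversight elsewhere. This also stands. It bears on size, not on whether such a patient would be counted.

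**Other outputs.** GHAS Change, RHI Change and Global RHI Score Change all measure change, and RHI Mucosal Healing inherits the SES-CD fall from Endoscopic Remission. They help the reader but do not correct the two patient-level proportions.

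**Missing text.** Table 6, which lists the proportion-based endpoints and methods, and Section 9.5 are not in the SAP text available to this review. A restricted patient-level row there cannot be ruled out.

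Three stronger readings are tempting and not supported.
- A reader might infer that the bias always favours the drug. It does so only when s > r. NRI lowers s, most of all at Week 52 after an optional extension.
- A reader might infer that the ITT proportion is wrong and should be demoted. It is a valid description of status at the visit; which analysis is called main is a preference.
- A reader might extend the point to CRP Response-10 and FCP Response-250. The list of endpoints that would settle this is blacked out, SAP 7.2.2 already tabulates baseline categories at both cut-offs, and Appendix 5 records an added CRP analysis restricted to patients at or above 10 mg/L at baseline.

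**Conclusion.** The point holds for patient-level RHI Remission and GHAS Remission as they stand in the visible SAP text. Status at the visit is enough, entry does not require histologic activity, and the existing baseline restriction covers only by-segment RHI endpoints.

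The size is unknown because p0 and s are not in the documents. For 3 to 12 baseline remitters among 60, r = 15% and s from 50% to 100%, all assumed apart from the planning rate, the excess runs from 1.75 to 17.0 points. Given the entry thresholds, the lower part of that range is more plausible. The effect is upward when baseline remitters are counted as remitters more often than active patients become so. It is a cheap improvement of low priority, subject to what Table 6 and Section 9.5 contain.

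**What to change.** First check SAP Table 6 and Section 9.5 for a patient-level restricted analysis. If there is none:

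1. In SAP 4.2.2 and Table 3, add patient-level RHI Remission and GHAS Remission among patients not in RHI (GHAS) remission at baseline, meaning that at least one measured baseline segment fails a Table 14 (Table 12) limit.
2. Present each beside the ITT/NRI proportion, with the number and percentage already in remission at baseline and the number with no baseline histology.
3. State that patients with no baseline histology are excluded from the restricted denominator and remain non-responders in the ITT analysis. Without this statement, their removal could raise the restricted rate unnoticed.

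The cost is a few lines of SAP text and some added table rows from data already collected. The added analysis has a smaller denominator and wider intervals. By the SAP 5.1 formula at 15%, the half-width rises from 9.03% with 60 patients to 1.96 × √(0.1275/54) = 9.52% with 54, and to 1.96 × √(0.1275/48) = 10.10% with 48. The ITT result is unchanged.
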